6.2.2.1 Analysis of the secondary efficacy variables

HMB response and absence of bleeding (spotting allowed) will be analyzed descriptively in frequency tables by treatment period and region within each treatment group. The time to event variables will be analyzed for each treatment group using Kaplan-Meier estimates (including number of events, number of censored subjects, median, 25th and 75th percentiles). Kaplan-Meier plots will also be presented.

Additionally, treatment groups A1 and B2 with vilaprisan treatment in TP1 will be pooled and results will be presented for this pooled population.

The first three secondary endpoints evaluated for TP1 are part of the testing hierarchy within the confirmatory analysis. The confirmatory analysis of these variables is described in the following.

HMB response

The first secondary efficacy variable HMB response (yes/no) will be analyzed analogously to the primary efficacy variable amenorrhea.

Time to onset of amenorrhea

The time to onset of amenorrhea can be described in terms of a hazard rate. The null hypothesis of no treatment effect with respect to the onset of amenorrhea (see Figure 6–2) can thus be stated as an equality of hazard rates $\lambda_{v,k}(t)$ and $\lambda_{p,k}(t)$ in the *k*-th stratum/region for the vilaprisan group (v) and the placebo group (p):

$$H_0: \lambda_{\nu,k}(t) = \lambda_{\mu,k}(t)$$
 for $k = 1, 2, 3, t \le \tau$,

where k corresponds to the strata/regions ($1 \cong US$, $2 \cong Japan$, and $3 \cong$ other) and τ is the largest observed event time in the pooled treatment groups used for the comparison.

In order to test the null hypothesis of no difference in time to onset of amenorrhea between vilaprisan 2mg and placebo versus the alternative hypothesis of a difference for at least one stratum/region, a logrank test stratified by region/country is conducted at a local 0.05 significance level.

The test statistic of the logrank test compares the observed number of events and the numbers of events expected under the null hypothesis in each treatment group per stratum. It is defined as

$$Z = \sum_{k=1}^{3} Z_{\nu,k}(\tau) / \sqrt{\sum_{k=1}^{3} \hat{\sigma}_{\nu,k}^{2}},$$

where in each stratum k, the values for $Z_{\nu,k}$ and $\hat{\sigma}_{\nu,k}$ are derived in the following way (the stratum index k is left out for all variables out of convenience):

$$Z_{\nu}(\tau) = \sum_{i=1}^{D} \left(d_{\nu,i} - Y_{\nu,i} \frac{d_i}{Y_i} \right) ,$$

$$\hat{\sigma}_{\nu}^2(\tau) = \sum_{i=1}^{D} \frac{Y_{\nu,i}}{Y_i} \left(1 - \frac{Y_{\nu,i}}{Y_i} \right) \left(\frac{Y_i - d_i}{Y_i - 1} \right) d_i$$

In these formulae, if $t_1 < \cdots < t_D = \tau$ are the distinct event times, i.e. times of onset of amenorrhea,

- the values of $d_{v,i}$ represent the number of events observed in the vilaprisan group at time point t_i
- $Y_{v,i}$ denotes the number of subjects at risk just prior to t_i in the vilaprisan group,
- d_i denotes the number of events observed in the vilaprisan group and placebo group combined at time point t_i and
- Y_i denotes the number of subjects at risk just prior to t_i in the vilaprisan group and placebo group combined [11].

The logrank test statistic Z asymptotically follows a standard normal distribution under the null hypothesis.

Time to onset of controlled bleeding

Time to onset of controlled bleeding will be analyzed analogously to the secondary efficacy variable time to onset of amenorrhea.

Absence of bleeding

Absence of bleeding (yes/no) will be analyzed descriptively with frequency tables by treatment period within each treatment group.

6.2.2.2 Sensitivity analyses of the secondary efficacy variables

Sensitivity analyses for the variables HMB response, time to onset of amenorrhea and time to onset of controlled bleeding will be conducted on the PPS analogously to the primary efficacy variable (see Section 6.2.1.2).

6.2.3 Further efficacy variables and analyses

All further variables will be presented by means of descriptive statistics based on the FAS population. Time to event variables will be analyzed using the Kaplan-Meier estimates (including number of events, number of censored subjects, median, 25th and 75th percentiles) and Kaplan-Meier plots will also be presented. For continuous variables, the number of observations, mean, median, standard deviation, minimum, and maximum as well as change from baseline will be computed. For categorical (dichotomous) variables the data will be presented using frequency tables. The data will be presented by treatment period and treatment group. Additionally, results for all patients receiving vilaprisan treatment for 12 weeks will be presented, i.e. results for TP1 of treatment groups A1 and B2 will be pooled.

The further efficacy variables and their analysis are outlined in the following subsections.

6.2.3.1 Binary bleeding variables

• Treatment success rate

The treatment success rate is defined as percentage of subjects who fulfill the criteria of HMB response (MBL <80.00 mL and >50% reduction in MBL as compared to baseline) and who have not been withdrawn from the study due to AEs, due to non-fulfillment of selection criteria (related to fibroid size or HMB at baseline), due to fibroid surgery having been performed during the study. Treatment success rate will be derived separately for the AH method and for MP.

Only fibroid surgeries that occur during the length of the originally planned study design (including FUP) prior to the temporary pause (Integrated Clinical Study Protocol, version 3.0, and protocol versions before) will be considered for deriving the treatment success rate. The FUP visit of the originally planned study design is on Day 7-15 of the 2nd menstrual cycle after the subject's end of treatment. That means that for subjects who have a prolonged FUP due to the temporary pause, the FUP according to the original study design will be derived. The derivation will be based on the end date of the subject's last treatment period and a follow-up time fixed to 12 weeks. Assuming a time to first menses after end of treatment of about 4 weeks and a cycle length of 4 weeks, 12 weeks of follow-up will cover at least the time period until the FUP visit would have been conducted according to the original study design.

Treatment success will be summarized with frequency tables by treatment period within treatment group. Number of observations and percentages will be presented.

• Amenorrhea

Amenorrhea, as further efficacy variable, is defined as MBL < 2 mL per 28 days of treatment for consecutive, non-overlapping 28-day periods not considered for the primary efficacy variable. An analogous approach as described for amenorrhea in the last 28 days of treatment (Section 6.2.1) will be applied to assess the amenorrhea status for each of the consecutive, non-overlapping 28-day periods within a treatment period (except for the 28-day period extension in case of missing values and criterion iii), which both do not apply).

In case of no premature discontinuation, amenorrhea will be evaluated for the first and second 28-day periods of the subject's TP1 and TP2 when the AH method is used. When the MP is used, amenorrhea will be evaluated in all non-overlapping 28-day periods of TP1 and TP2. Only subjects with completed 28-day periods will be considered for the analysis of amenorrhea in those 28-day periods.

In addition, amenorrhea will be analyzed for an incomplete period which does not comprise 28 days. This analysis is based on all subjects for whom the length of the treatment period is not a multiple of 28 days. The reason for this might be premature discontinuation from the study or prolonged treatment.

Amenorrhea will be summarized by a frequency table by (pooled) treatment group and the 28-day periods grouped by treatment period.

• HMB response

HMB response, as further efficacy variable, is defined as MBL <80.00 mL per 28 days of treatment and >50% reduction from baseline where MBL is assessed for consecutive, non-overlapping 28-day periods not considered for the secondary efficacy variable. An analogous approach as described for HMB response in the last 28 days of treatment (Section 6.2.2) will be applied to assess HMB response for each of the consecutive, non-overlapping 28-day periods within a treatment period (except for the 28-day period extension in case of missing values and criterion ii), which both do not apply).

In case of no premature discontinuation, HMB response will be evaluated for the first and second 28-day periods of the subject's TP1 and TP2 when the AH method is used. When the MP is used, HMB response will be evaluated in all non-overlapping 28-day periods of TP1 and TP2. Only subjects with completed 28-day periods will be considered for the analysis of HMB response in those 28-day periods. In addition, HMB response will be analyzed for an incomplete period which does not comprise 28 days. This analysis is based on all subjects for whom the length of the treatment period is not a multiple of 28 days. The reason for this might be premature discontinuation from the study or prolonged treatment.

HMB response will be summarized by a frequency table by (pooled) treatment group and the 28-day periods grouped by treatment period.

6.2.3.2 Time to onset variables

The time to onset variables described in the following will be analyzed analogous to the descriptive analysis described in Section 6.2.2.1, namely by Kaplan-Meier estimates and Kaplan-Meier plots for all regions combined.

• **Time to onset of amenorrhea** and **time to onset of controlled bleeding** (see Section 6.2.2)

These variables will be assessed by the MP separately for TP1 and TP2.

• Time to start of bleeding after last study drug intake

The start of bleeding after last study drug intake is defined by the first day for which bleeding intensity is "mild" or higher according to the UF-DBD. Only data from the UF-DBD will be considered to determine "start of bleeding after last study drug intake" because UF-DBD data are typically available even if there are missing values for one or both of the other two methods (MP, AH method).

The last study drug intake refers to the end of TP1 and the end of TP2, as defined in Section 4.5 ("Treatment period").

If an endometrial biopsy was conducted during the evaluation time period, any bleeding reported on the day of biopsy and the 3 days thereafter will not be considered in this evaluation, that is, if a bleeding intensity is reported on these days, the bleeding intensity will be overwritten to "no vaginal bleeding".

If a subject did not experience a start of bleeding, she will be censored at latest available date from the bleeding eDiary data from the UF-DBD. If bleeding has to be induced, subjects will be censored on the date of bleeding induction. For the analyses after TP1, the subject will be censored at latest at TP2 start date if she starts TP2.

6.2.3.3 Volume of menstrual blood loss (MBL) related variables

The following variables related to volume of MBL will be evaluated both on the AH method and the MP:

- Volume of MBL per 28 days: Volume of MBL will be derived for each nonoverlapping 28 days within a treatment period based on subjects who entered the respective 28-day period.
- Volume of MBL per bleeding episode for the first, second, and if applicable third bleeding episode after the end of treatment.
- Volume of MBL per bleeding episode within the treatment break. All days of the bleeding episodes will be used even if some days of the episode lie outside the treatment break. The first, second and third bleeding episode will be considered.
- Percentage of subjects with ≥ 50% reduction in MBL per each non-overlapping 28day periods compared to baseline (based on subjects who entered the respective 28day period).

Bleeding on the day of biopsy and the 3 days thereafter will not contribute to the MBL in this evaluation. Analysis of volume of MBL will be done by treatment group separately for TP1, break period, TP2 and FUP. An incomplete period which does not comprise 28 days will be analyzed for any of TP1, break period, TP2 and FUP. The analysis of this incomplete period

is based on all subjects for whom the length of the considered time period (TP1, break period, TP2 or FUP) is not a multiple of 28 days. A subject's data from the last x < 28 days of the considered time period will be included.

6.2.3.4 Ultrasound examination related variables

The following variables will be presented by (pooled) treatment group and by Intervals B as well as by post-baseline visit (i.e. Visit 4, Visit 5, Visit 6, EoT visit, FUP visit, safety closeout visit):

- Percent change in the sum of the volume of the 3 largest fibroids compared to baseline (measured by ultrasound). If less than 3 fibroids are present, the volume of the actual number of fibroids will be summed.
- Percentage change in volume of the largest fibroid from baseline (measured by ultrasound)
- Percent change in volume of uterus compared to baseline (measured by ultrasound)
- Percentage of subjects with a reduction of $\geq 25\%$ of the sum of the volume of the 3 largest fibroids compared to baseline (measured by ultrasound). If less than 3 fibroids are present, the volume of the actual number of fibroids will be summed.
- Percentage of subjects with a volume reduction of ≥ 25% of the largest fibroid compared to baseline (measured by ultrasound)
- Percentage of subjects with a reduction of $\geq 25\%$ of uterine volume compared to baseline (measured by ultrasound)

If multiple volume assessments are available for a time period, the smallest volume measurement will be used for the Baseline time period, and the largest volume measurement will be used for any other time periods of Intervals B.

6.2.3.5 Uterine fibroids surgeries

The number and proportions of subjects undergoing surgical treatment for uterine fibroids will be displayed in a frequency table by treatment group and by the following time periods: treatment period, break period, FUP (including prolonged FUP). In contrast to other efficacy variables, any fibroid surgeries performed during FUP of patients who did not start TP2 will be evaluated for FUP rather than for break period.

6.2.3.6 Patient-reported outcome and Clinician-reported outcome

Change in UF-DSD individual items compared to baseline

The UF-DSD is a newly developed multi-item PRO instrument designed to assess cardinal symptoms of uterine fibroids using a 24-hour recall period.

The UF-DSD includes 2 items (items 1 and 2) to assess swelling and bloating symptoms in the abdomen and pelvic area using a 5-graded Likert-type severity rating ('no symptom' to 'very severe symptom'), and 2 items (items 3 and 4) using a 0 to 10 numerical rating scale to assess pain at its worst in the abdominal/pelvic and lower back areas respectively, with 0 indicating 'no pain' and 10 'pain as bad as you can imagine'. Additionally, item 5 assess the

intake of pain medication using a 4-point verbal rating scale ("no"; "yes, over the counter (non-prescription) pain medication"; "yes, prescription pain medication"; or "yes, both (over the counter and prescription pain medication"). Further information can be found in Appendix 3).

The following variables in each domain will be summarized by treatment group. Mean values will be evaluated per 28-day period within each of the following time periods: screening, baseline (only the last 28 days before first study drug intake), 1st 28-day period, 2nd 28-day period, 3rd 28-day period for any of TP1, break, TP2, FUP1, FUP2, etc.. Absolute changes from baseline will be provided as well. Graphical displays will also be provided.

Bulk symptoms (items 1 and 2):

- Mean of subjects' relative frequencies (relative frequency is calculated for each subject as ratio of given severity to all severities) of the symptom scores
- Mean of subjects' symptom scores of the 7 days with worst assessment (i.e., highest score)

Pain (items 3 and 4):

- Mean numerical rating pain score
- Mean numerical rating pain score of the 7 days with worst pain (i.e., highest score)

Pain medication (item 5):

• Proportion of days with pain medication intake

Change in UFS-QoL scores compared to baseline

The UFS-QoL is a widely used disease-specific instrument that assesses symptom severity and health-related quality of life (HRQoL) in subjects with uterine fibroids [12].

It consists of 37 items including an 8-item symptom severity scale and 29 health-related quality of life questions comprising 6 subscales: concern, activities, energy/mood, control, self-consciousness, and sexual function which are responded to using a recall period of 3 months. All items are scored on a 5-point Likert scale, ranging from "not at all" to "a very great deal" for symptom severity items and "none of the time" to "all of the time" for the HRQoL items.

Symptom Severity, Activities, Revised Activities, HRQoL subscale scores and revised HRQoL scores are summed respectively and transformed into a 0-100-point scale each. The Symptom Severity scale and the HRQoL subscale scores are inversely related with higher Symptom Severity scores indicating greater symptoms while higher HRQoL subscale scores indicate better HRQoL.

Details can be found in Appendix 4.

For each subscale (including the symptom severity scale), raw scores and transformed scores will be summarized using descriptive statistics within treatment group by visit (Visit 3, Visit 5, EoT visit and FUP visit), as well as the absolute change from baseline. The time course for each subscale (raw scores and transformed scores) by visit and by treatment group will be shown using line plots depicting the mean \pm standard deviation.

Change in CGI-I scores compared to baseline

The Clinical Global Impression (CGI-I) is a widely used single item questionnaire which asks the investigator to describe the subject's overall severity of uterine fibroids symptoms. The verbal response options for CGI-I are:

- None
- Very mild
- Mild
- Moderate
- Severe
- Very severe

Each item will be summarized by a frequency table with the number of observations and percentage for each treatment group. CGI-I is recorded at Visit 3 (baseline), EoT visit and FUP visit. CGI-I assessments will be shown by visit. Graphical displays of scores at the three visits will also be provided.

The change from baseline to EoT visit and FUP visit, respectively, will be analyzed using shift tables.

6.2.3.7 Variables related to laboratory parameters

Intervals C will be used for the following assessments:

- Change from baseline in hemoglobin, hematocrit, and ferritin: Absolute change from baseline will be summarized using descriptive statistics and displayed by time period within treatment group.
- Percentage of subjects with normal hemoglobin >12 g/dL and normal hematocrit >36% :

Frequency tables with number of observations and percentage will be displayed by time period within treatment group.

If multiple measurements for a patient are available for any of the parameters during a time period, the smallest value is used in the analysis, as specified in Appendix 5.

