### **Evaluation plan for subjects with unusual HMB or bleeding pattern**

The evaluation should include the following assessments:

- Comparison of subject’s subjective report with documented bleeding pattern and amount of blood loss (UF-DBD, MP, and/or AH method, if available from the months preceding the safety closeout visit).
- Unscheduled ultrasound
- In case of HMB or prolonged bleeding, unscheduled blood sample to assess for anemia
- Possible contributing factors (eg, new concomitant medication, variability of disease, perception of increased HMB after period of amenorrhea)

An unscheduled endometrial biopsy should be conducted in case of

- Endometrial thickness (double layer) > 18 mm and/or
- Clinical suspicion of relevant endometrial pathology

Further follow-up measures will be determined by the outcome of the endometrial biopsy (see Section 9.6.3.2.5).

HMB should be recorded as an AE only as specified in Section 9.6.1.6. If HMB fulfills the criteria of an SAE (see Section 9.6.1.1), if needed, an appropriate treatment as per local standard of care (eg, curettage) is to be performed.

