## 10. Statistical methods and determination of sample size

### 10.1 General considerations

Statistical analyses will be conducted by or under the supervision of the sponsor's study statistician, except for the analysis of PK/PD data, which will be performed and reported under the supervision of the sponsor's pharmacometrics group.

Statistical analyses will be performed using Statistical Analysis Software (SAS Institute Inc., Cary, North Carolina, USA). The SAS version and further details on the statistical analyses will be provided in the SAP that will be approved before database release.

All target variables will be described according to their type using descriptive statistics frequencies or mean, standard deviation (SD), minimum, maximum, median, first and third quartiles. Where appropriate, the individual change from baseline to end of treatment will also be analyzed.

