- Percentage of subjects undergoing surgical treatment for uterine fibroids
- Change in UF-DSD individual items compared to baseline
- Change in UFS-QoL scores compared to baseline
- Change in CGI\_I scores compared to baseline.
- Change from baseline in hemoglobin, hematocrit, and ferritin
- Percentage of subjects with normal hemoglobin >12 g/dL and normal hematocrit >36%

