Baseline values and changes from baseline: If an analysis is performed by visits or by Intervals 'Exit Examination' (see *Time Intervals*), the last valid, non-missing value prior to the Reference start date will be considered as baseline value. If the analysis is performed by any time interval different than Intervals 'Exit Examination', the 'worst' measurement will be used, whereby 'worst' is defined for the considered parameter within the specific section.

(*Absolute*) *changes from baseline* will be calculated as the difference between the post-baseline value and the baseline value:

Absolute change = post baseline value - baseline value.

Relative changes from baseline, also referred to as *percent change from baseline*, are derived for some variables. It is defined as

Relative change = $100 \times [\text{post baseline value} - \text{baseline value}] / \text{baseline value}$.

Those baseline definitions apply to the analysis of all TPs. For variables analyzed by 28-day periods, the baseline period corresponds to the last 28 days before Reference start date. This definition does not apply to baseline MBL volume where a specific definition is provided in this section (see *Baseline menstrual blood loss*).

Bleeding episode (assessed by the UF-DBD): A bleeding episode is defined as day(s) with bleeding/'spotting' of which at least one day is of intensity 'mild' or higher, preceded and followed by at least 2 consecutive days with eDiary entry 'no vaginal bleeding'. The preceding 2 bleeding-free days may not be recorded for the first bleeding episode at study entry [1].

This definition of bleeding episode, based on the UF-DBD, will be implemented in the analysis to identify bleeding episodes. The protocol includes a definition of bleeding episode based on the AH method, which will be implemented during the screening period to facilitate the assessment of the HMB inclusion criterion (criterion 5, MBL >80 mL) by clinical sites. This latter definition of bleeding period will not be used in the statistical analysis.

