6.4.2.7 Anemia

Frequency presentations will be provided for moderate to severe anemia with hemoglobin $\leq 10.9 \text{ g/dL}$. Frequency tables with number of subjects and percentage will be displayed within treatment group and by Intervals C. If a subject has more than one hemoglobin measurement within a time interval of Intervals C, the smallest value (i.e. worst) will be used.

A listing will be provided for subjects with abnormal values.

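### Hemoglobin, hematocrit and ferritin are summarized as efficacy variables by the smallest value per period, so results for women with several values depend on how often and when blood was drawn

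*SAP*

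**What the plan says.** Protocol 10.3.1.3 lists "Change from baseline in hemoglobin, hematocrit, and ferritin" among the other efficacy variables, together with the percentage of women with hemoglobin above 12 g/dL and hematocrit above 36%. SAP 6.2.3.7 sets out their analysis: "Intervals C will be used for the following assessments". In Intervals C (SAP 4.5, Figure 4–1) each treatment period is a single window, as are baseline and the break. The rule within a window is: "If multiple measurements for a patient are available for any of the parameters during a time period, the smallest value is used in the analysis", with a reference to Appendix 5.

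The baseline is handled the same way. SAP 4.5 says: "If the analysis is performed by any time interval different than Intervals 'Exit Examination', the 'worst' measurement will be used", and it leaves each section to define worst. For these variables that is the smallest value.

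SAP 6.4.2.7 applies the same convention to the anemia safety table, where "the smallest value (i.e. worst) will be used".

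Protocol 10.1 says in general terms: "Where appropriate, the individual change from baseline to end of treatment will also be analyzed". For these three parameters the SAP plans no summary by visit or at the end of treatment. Other efficacy families do get one: ultrasound by visit as well as by interval (SAP 6.2.3.4), and UFS-QoL by visit and CGI-I as a shift to the EoT visit (both SAP 6.2.3.6).

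**The concern.** Taking the worst value in an interval is a safety convention. SAP 6.4.2.3 uses it to make sure no abnormal value is missed. As an efficacy summary it answers a different question. A reader of a change-from-baseline table will want to know where hemoglobin stood after 12 weeks of treatment. The planned table gives the lowest value seen in those weeks minus the lowest value seen before them.

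This matters in two ways when a woman has more than one value in a window. If hemoglobin rises during treatment, the smallest value tends to be an early one, taken before much of the rise. Even without a trend, the minimum of several noisy values lies below a single value on average. Two women with the same true course can then show different results because one had more blood samples, and the table does not reveal this.

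**Working it through.** The plan gives no effect size, SD or sample size for these variables, so there is no figure of its own to reproduce. The check is in two parts: whether several values per window are to be expected, and how much the rule moves the result if they occur.

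**How many values per window**
- The only treatment-phase schedule shown is in the Amendment 1 log (Protocol 15.1.2.4, Table 9–1, new text). It has one blood draw per treatment period: Visit 5 in TP1 and the EoT visit in TP2, each at Day 78–84. There is none at Visit 4 or Visit 6. Under that schedule the smallest TP1 value is the end-of-treatment value.
- Version 3.0 added Visits 4.1, 5.1 and 6.1 (Protocol 15.2) and monthly liver parameters on treatment (Protocol section 5, liver monitoring). Whether hemoglobin, hematocrit or ferritin were measured at those draws is not shown.
- SAP 6.4.2.3 counts unscheduled laboratory values, and 6.2.3.7 does not exclude them.

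So several on-treatment values are possible, but their frequency cannot be read from the documents.

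**Size when they occur**

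Assumptions, none from the documents: true baseline hemoglobin with mean 10.5 g/dL and between-woman SD 1.3; within-woman SD *s* of 0.3, 0.5 or 0.8; a linear rise *g* over 84 days; the scheduled sample at Day 81; extra samples on random days. Results marked as simulated come from 200,000 simulated women per setting.

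1. One sample per window, *g* = 2: expected change = 2 × 81/84 = **+1.93 g/dL**. Share above 12: the total SD is √(1.3² + 0.5²) = 1.39 and the mean is 10.5 + 1.93 = 12.43, so Φ(0.43/1.39) ≈ **62%**. The rule has no effect here.

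2. Several samples, *g* = 2, *s* = 0.5, one baseline value (simulated):

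| Samples in the window | Mean change, smallest value | Hemoglobin above 12 |
|---|---|---|
| Day 81 only | +1.93 | 62% |
| Day 81 plus one extra | +0.93 | 35% |
| Day 81 plus two extra | +0.55 | 25% |
| Days 28, 56 and 81 | +0.59 | 26% |

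Without noise, the Day 28 value alone gives 2 × 28/84 = +0.67. For Days 28/56/81 the simulated change runs from +0.66 (*s* = 0.3) to +0.44 (*s* = 0.8). With *g* = 1 and *s* = 0.5, the change is +0.96 for one sample and +0.15 for Days 28/56/81.

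3. No true change, one baseline value: the shift is the expected minimum of *n* standard normal values times *s*. That expectation is about −0.56 for *n* = 2 and −0.84 for *n* = 3. At *s* = 0.5, one extra sample lowers the mean by **0.28 g/dL** and two extra by **0.42 g/dL**. Over *s* = 0.3 to 0.8 the ranges are 0.17 to 0.45 and 0.25 to 0.67.

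4. Baseline also a minimum, two baseline values, *s* = 0.5, *g* = 2: the baseline falls by 0.28, so the change rises by the same amount. One on-treatment value gives 1.93 + 0.28 = **+2.21**, an overstatement. Days 28/56/81 give **+0.88** (simulated), still well below +1.93.

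**Direction**
- Percentage: the smallest value cannot exceed the last value, so the share above a threshold can only fall or stay the same. The baseline rule does not offset this.
- Change: it can go either way, depending on how many values fall before and during treatment.
- Between arms: early samples taken before recovery would understate vilaprisan. More samples on placebo would overstate the contrast. The documents do not settle which dominates.

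**The case against.** The rule acts only when several measurements exist, and under the one visible schedule there is a single draw late in each treatment period. A reader might infer that the planned tables hide recovery by the end of treatment for women in general. The documents do not support that: with one value per window the table shows the end-of-treatment value, and monthly hemoglobin sampling is an assumption.

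A reader might also infer that placebo women look worse because bleeding triggers extra samples. Protocol 9.6.3.2.7 does call for an "unscheduled blood sample to assess for anemia" in cases of heavy or prolonged bleeding. However, the criteria leading to it are headed as applying to the temporary pause, when women could finish a treatment period but not start one (SAP section 3). Such samples fall mainly in follow-up. They enter the statistics only if analyzed centrally (Protocol 9.6.3.1; SAP 6.4.2.3), and no passage says that they are more frequent on placebo.

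Nor is a protocol rule broken. The sentence in Protocol 10.1 is general and conditional, and worst-value selection by interval is a declared SAP convention, also used for fibroid and uterine volume in SAP 6.2.3.4. The variables are descriptive and stand outside the four-test hierarchy (Protocol 10.3.2.2; SAP 6.2).

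All of this stands as a limit on scope and weight. It does not remove the core point. Where several values exist, the result depends on sampling, and no second summary lets a reader see that. The ultrasound variables have such a summary, by visit.

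**Conclusion.** The point holds in conditional form. For women with more than one value in an Intervals C window, SAP 6.2.3.7 makes both the change from baseline and the percentage above threshold depend on the number and timing of samples. The percentage is biased downward relative to the end-of-treatment value. The change may be biased in either direction because baseline is also a minimum. The between-arm direction is undetermined.

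Under the stated assumptions, the same true rise of 2 g/dL appears as anything from +2.21 to +0.55 g/dL at a within-woman SD of 0.5, and sampling alone can shift a stable mean by 0.28 to 0.42 g/dL. These sizes rest on assumed inputs, and the share of women affected is unknown. Alpha, power and the study's success criterion are untouched. This is a cheap improvement to a descriptive display, not a flaw in the confirmatory analysis.

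**What to change.** In SAP 6.2.3.7, for hemoglobin, hematocrit and ferritin, summarize the last central-laboratory value at the end of each treatment period against the last non-missing value before first dose. For TP1 this is the Visit 5 value, or the EoT-visit value for women who stopped early or did not start TP2; for TP2 it is the EoT-visit value. Naming Visit 5 alone would miss women whose EoT visit followed TP1, a case that SAP 4.1 foresees. State explicitly that this is an exception to the interval baseline rule in SAP 4.5. Use the same values for the percentage with hemoglobin above 12 g/dL and hematocrit above 36%.

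The new summary may replace the smallest-value display or stand beside it. Keep the smallest-value rule for the anemia safety table in SAP 6.4.2.7, where it fits the purpose.

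The cost is a short SAP edit and, if both displays are kept, one added table. No new data are needed.
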